5.4.2 IGA mod 2011

IGA mod 2011 consist of 4 response items, each response lead to an IGA mod 2011 score as follows:

Response (short description)	Score
Clear	0
Almost clear	1
Mild	2
Moderate	3
Severe	4

[figure not shown]
An IGA mod 2011 0/1 responder is defined as a patient achieving a score of 0 or 1 and improve by at least 2 points on the IGA scale at post-baseline compared to baseline.

5.4.3 BSA and PASI

The **BSA** score and the **PASI** score will be analyzed as calculated by the tablet. The PASI improvement and PASI responder status will be derived as follows, based on the baseline value as defined in [Section 2.1.1](#).

PASI improvement ratio (%) = percent change from baseline = $(\text{baseline PASI score} - \text{post-baseline PASI score}) / (\text{baseline PASI score}) * 100$

A PASI xx responder is defined a patient achieving a PASI improvement ratio of at least xx % with xx = 50, 75, 90 and 100.

5.4.5 HAQ-DI

The HAQ-DI consists of 20 items in 8 categories of functioning including dressing and grooming, arising (getting up), eating, walking, hygiene, reach, grip, and usual activities. Responses to each item are scored as follows:

Response	Score
Unable to do	3
With much difficulty	2
With some difficulty	1
Without any difficulty	0

Each of the 8 categories has a companion question about the use of 'aids or equipment' and 'help from another person' to supplement the answers given to the items of the respective category.

Category	Items "Aids or equipment"	Help from another person
A: Dressing & Grooming	Aids used for dressing	Dressing & Grooming
B: Getting up	Specially adapted chair	Getting up
C: Eating	Specially adapted utensils	Eating
D: Walking	Walking stick	Walking
	Walking frame	
	Crutches	
	Wheelchair	
Categories A - D	Other A - D	
E: Hygiene	Bath seat	Hygiene
	Raised toilet seat	
	Long-handled appliances in bathroom	
	Bath rail	
F: Reach	Long-handled for reaching things	Reaching
G: Grip	Jar opener	Gripping and opening things
H: Activities		Shopping and housework
Categories E - H	Other E - H	

The score for each of the 8 categories is the maximum score of the corresponding items. If items are missing the category score is derived from the remaining answered items. If an item of 'aids or equipment' or 'help required from another person' is ticked and this item is not 'other', the score for the corresponding category is the maximum out of 2 and the maximum score of the items of that category.

The disability index will be calculated as the mean score of the 8 category scores. If one of the 8 scores is missing the mean over the 7 available scores will be derived. If more than two category scores are missing the disability index not be calculated.

5.4.6 EQ-5D

The EQ-5D consists of an EQ-5D[®] descriptive system and the EQ-5D[®] VAS.

The EQ-5D[®] descriptive system comprises the following 5 dimensions: mobility, self-care, usual activities, pain/discomfort and anxiety/depression. The 5 dimensions have 5 response levels scored from 1 to 5. The first 3 dimensions have the response levels lasting from no problems, slight problems, moderate problems, severe problems to unable, the last 2 dimensions have the 5 response levels lasting from no, slight, moderate, severe to extreme.

From these 5 dimensions the Crosswalk-index will be calculated by concatenating the responses and choosing the corresponding country specific index value from the EQ-5D-5L_Crosswalk_Index_Value_Calculator.v2 excel file. For countries where the Crosswalk index value is not defined, the index value of the country as specified below will be used.

Country	Crosswalk index country to use
Belgium	UK
Bulgaria	UK
Czech Republic	UK
Estonia	UK
France	France
Germany	Germany
Greece	UK
Hungary	UK
Israel	UK
UK	UK
Italy	UK
Latvia	UK
Lithuania	UK
Poland	UK
Portugal	UK
Romania	UK
Russia	UK
Slovakia	UK
Spain	Spain

The any of the 5 dimensions is missing the Crosswalk index will not be calculated.

The VAS is a continuous scale starting from 0 (worst possible health state) to 100 (best possible health state). The VAS will be analyzed as entered by the patient.

5.4.7 TSQM

The TSQM consists of 9 questions. The responses are scored as follows:

Response	Score	Response	Score	Response	Score
Extremely dissatisfied	1	Extremely difficult	1	Extremely inconvenient	1
Very dissatisfied	2	Very difficult	2	Very inconvenient	2
Dissatisfied	3	difficult	3	Inconvenient	3
Somewhat satisfied	4	Somewhat easy	4	Somewhat convenient	4
Satisfied	5	Easy	5	Convenient	5
Very satisfied	6	Very easy	6	Very convenient	6
Extremely satisfied	7	Extremely easy	7	Extremely convenient	7
Not at all confident	1	Not at all certain	1		
A little confident	2	A little certain	2		
Somewhat confident	3	Somewhat certain	3		
Very confident	4	Very certain	4		
Extremely confident	5	Extremely certain	5		

The TSQM scale scores for effectiveness, convenience and global satisfaction will be derived. If more than one question for a score remains unanswered the corresponding score will not be calculated.

Effectiveness score = $([\text{Score question 1} + \text{score question 2} + \text{score question 3}] - 3) / 18 * 100$

If one of the questions remains unanswered the score will be derived as

$= ([\text{Score question 1 or 2} + \text{score question 2 or 3}] - 2) / 12 * 100$

Convenience score = $([\text{Score question 4} + \text{score question 5} + \text{score question 6}] - 3) / 18 * 100$

If one of the questions remains unanswered the score will be derived as

$= ([\text{Score question 4 or 5} + \text{score question 5 or 6}] - 2) / 12 * 100$

Global satisfaction score

$= ([\text{Score question 7} + \text{score question 8} + \text{score question 9}] - 3) / 14 * 100$

If one of the questions 7 or 8 remains unanswered the score will be derived as

$= ([\text{Score question 7 or 8} + \text{score question 9}] - 2) / 10 * 100$

If question 9 remains unanswered the score will be derived as

$= ([\text{Score question 7} + \text{score question 8}] - 2) / 8 * 100$

5.4.8 PBI

The questionnaire includes 27 items on patient-relevant therapy needs and benefits. The first part of the instrument, the 'Patient Needs Questionnaire' (PNQ), is filled in by the patients before therapy. A 5-step Likert scale (0 = 'not important at all' to 4 = 'very important') records the individual relevance of the different items to the patients. The second part, the PBQ, is filled in by the patients during or after therapy. It comprises the same items as the PNQ, but in contrast, the patients evaluate the extent to which the treatment needs have been fulfilled by therapy (scaled from 0 = 'treatment did not help at all' to 4 = 'treatment helped a lot'). In addition, the Likert scale contains the option 'does not apply to me' in the PNQ and the option 'did not apply to me' in the PBQ. The needs prior to treatment (PNQ) and the benefits achieved by treatment (PBQ) are converted to a weighted index value, the PBI.

$$PBI = \sum_{i=1}^k \frac{PNQ_i}{\sum_{i=1}^k PNQ_i} PBQ_i$$

Algorithm for the computation of the PBI global benefit value with k preference items (PNQ) and benefit items (PBQ); possible range of item values and global score values: 0-4.

[PBI Short Manual]

For the score calculation, both "does not apply" and "question unanswered" will be treated as missing values. The global score will be calculated using all items pairs (importance + benefit) for which the patient has given a response other than "does not apply". If more than 6 item pairs are missing the PBI will not be calculated.

5.5 Metabolic syndrome

Metabolic syndrome is defined if the patient is fulfilling the criteria for obesity and 2 of the following 4 additional criteria [[International Federation of Diabetes, 2006](#)]:

- raised triglycerides ≥ 150 mg/dL (1.7 mmol/L), or specific treatment for this lipid abnormality (Note: defined as intake of any medication of ATC class C10 at the time point of the evaluation)
- reduced HDL cholesterol < 40 mg/dL (< 1.03 mmol/L for men) or < 50 mg/dL (< 1.29 mmol/L for women, or specific treatment for this lipid abnormality (Note: defined as intake of any medication of ATC class C10 at the time point of the evaluation)
- raised blood pressure ≥ 130 mmHg (systolic) and / or ≥ 85 mmHg (diastolic), or treatment of previously diagnosed hypertension (Note: defined as intake of any medication of ATC classes C02, C03, C07, C08, C09 and reason for use is one of the terms selected by clinical review as per project-specific excel spreadsheet at the time point of the evaluation)
- raised fasting plasma glucose > 100 mg/dL (5.6 mmol/L), or previously diagnosed diabetes mellitus type 2

- Obesity is assumed when BMI is >30 kg/m² or in the following cases

Ethnic group	Waist circumference
Europids; Sub-Saharan Africans; Eastern Mediterranean and Middle East (Arab populations) – defined as subjects of Caucasian race and	Male >= 94 cm Female >=80 cm
South Asians, Chinese, Japanese, Ethnic South and Central Americans	Male >= 90 cm Female >=80 cm

In the present study the following rules for assignments to the above ethnic groups will be followed:

Ethnic group	Assignment using race from eCRF
Europids; Sub-Saharan Africans; Eastern Mediterranean and Middle East (Arab populations)	Race Caucasian, Black or Other.
South Asians, Chinese, Japanese, Ethnic South and Central Americans	Race Asian

5.6 Statistical models

5.6.1 Primary analysis

The primary analysis of this study will be descriptive without any formal group comparisons or hypothesis testing.

Summary statistics for discrete variables will be presented in contingency tables and will include absolute and relative frequencies. Confidence intervals will be derived as well based on the score method including continuity correction [Newcombe (1998)]:

With z as (1-alpha/2)-quantile of the standard normal distribution (SAS: $z=PROBIT(1-alpha/2)$), n as total number of subjects (i.e. number of subjects in the denominator), and p as estimated crude incidence (number of subjects with event / n) it is $q = 1-p$.

Then the lower limit is for $p > 0$, ($L = 0$ for $p = 0$),

$$L = \max \left(0, \frac{2np + z^2 - 1 - z \sqrt{z^2 - 2 - \frac{1}{n} + 4p(nq + 1)}}{2(n + z^2)} \right)$$

and the upper limit is for $p < 1$, ($U = 1$ for $p = 1$)

$$U = \min \left(1, \frac{2np + z^2 + 1 + z \sqrt{z^2 + 2 - \frac{1}{n} + 4p(nq - 1)}}{2(n + z^2)} \right)$$

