3.1 Study design

The study will utilize an open-label, prospective, non-randomized but stratified multicenter study design. The study will take place across Europe, in approximately 250 study centers in 30 European countries. The study will be implemented in both hospital-based and office-based settings; secukinumab is intended for use under the guidance and supervision of a physician experienced in the diagnosis and treatment of psoriasis and whose center fulfills ICH Good Clinical Practice (GCP) quality requirements for the conduct of clinical trials ([CHMP/EWP/2454/02 corr](#)).

[figure not shown]
Eligible patients will be categorized at Baseline according to previous exposure to treatment in one of the following 3 subpopulations:

- **Subpopulation A:** Patients who are **naïve to any systemic treatment**, e.g. patients failing or intolerant to previous topical treatment, including narrow band UVB, but never exposed to any systemic treatment, with or without contraindications to the use of conventional systemic treatment and in a need of a first systemic treatment.
- **Subpopulation B:** Patients who have been **previously exposed to at least one conventional systemic therapy**; either because of failure or intolerance to their previous conventional systemic treatment, they are in a need of a first biologic systemic treatment;
- **Subpopulation C:** Patients who have been **previously exposed to at least one biologic systemic therapy**; either because of failure or intolerance to their previous biologic systemic treatment, they are in a need of a different biologic systemic treatment.

All patients are scheduled to receive s.c. injections of secukinumab 300 mg at Week 0, 1, 2 and 3 during the first 4 weeks followed by monthly maintenance dosing of 300 mg secukinumab starting at Week 4 until Week 48. Consideration should be given to discontinuing treatment in patients who have shown no response up to 16 weeks of treatment (e.g. patients who did not achieve a PASI 50 response). If discontinued, patients will complete the end of study visit assessments. Some patients with an initially partial response (e.g. patients who achieve a PASI 50 response but not a PASI 75 response) may subsequently improve with continued treatment beyond 16 weeks.

The primary endpoint is the proportion of patients achieving a DLQI 0/1 response at Week 16 in the 3 pre-defined subpopulations and in the overall study population. The study design is presented in [Figure 3-1](#).

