6.4.1 Investigator's global assessment (IGA mod 2011)

The IGA mod 2011 will be conducted for overall psoriatic disease as indicated in the assessment schedule in [Table 6-1](#). It is recommended that the same evaluator conducts the assessment throughout the study wherever possible.

The IGA mod 2011 used in this study is static, i.e. it refers exclusively to the patient's disease state at the time of the assessments, and does not attempt a comparison with any of the patient's previous disease states, whether at Baseline or at a previous visit.

The IGA mod 2011 rating scale for overall psoriatic disease is shown in [Table 6-3](#).

Patients require an IGA mod 2011 score at Baseline of 3 or 4 in order to participate in the study. Based on this scale, a patient will be considered as an IGA 0 or 1 responder if they achieve a score of 0 or 1 and improve by at least 2 points on the IGA scale at a given time point compared to their score at Baseline.

The IGA mod 2011 score will be recorded in the eCRF.

[figure not shown]

Table 6-3 The IGA mod 2011 rating scale

Score	Short description	Detailed description
0	Clear	No signs of psoriasis. Post-inflammatory hyperpigmentation may be present.
1	Almost clear	Normal to pink coloration of lesions; no thickening; no to minimal focal scaling.
2	Mild	Pink to light red coloration; just detectable to mild thickening; predominantly fine scaling.
3	Moderate	Dull bright red, clearly distinguishable erythema; clearly distinguishable to moderate thickening; moderate scaling.
4	Severe	Bright to deep dark red coloration; severe thickening with hard edges; severe / coarse scaling covering almost all or all lesions.

Note: Involvement of nails is not part of the assessment

6.4.2 Assessment of psoriasis area and severity index (PASI) and total body surface area (BSA)

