2.1 Data analysis general information

The statistical analysis of the study (including the interim analysis) will be performed by [REDACTED], a designated Contract Research Organization (CRO).

SAS version 9.3 or later will be used to perform all data analyses and to generate tables, figures and listings.

Qualitative data (e.g., gender, race, etc.) will be summarized by means of contingency tables; a missing category will be included as applicable. Percentages will be calculated using the number of patients in the relevant population or subgroup as the denominator.

Quantitative data (e.g., age, body weight, etc.) will be summarized by appropriate descriptive statistics, i.e., n, mean, standard deviation (SD), first quartile (Q1), median, third quartile (Q3), minimum, and maximum.

Data from all study centers will be pooled for the analysis.

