2.5.2 Statistical hypothesis, model, and method of analysis

The primary analysis of this study will be descriptive without any formal group comparisons or hypothesis testing. The absolute and relative frequencies of patients achieving a DLQI 0/1 response, i.e. a DLQI score of 0 to 1, at Week 16 will be calculated for the subpopulations as well as for the overall study population. For the proportions, (descriptive) 95% CIs will additionally be reported.

The proportion of DLQI 0/1 response at Week 16, overall and by subpopulation, will be presented graphically.

Details how to derive the DLQI score are given in the [Appendix 5.4.1](#).

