2.14 Interim analysis

An interim analysis describing the self-reported baseline characteristics and HR-QoL of patients prior to treatment will be performed for this study after LPFT.

The interim analysis will be based on the Safety set.

Patient screening phase disposition, demographics, baseline disease characteristics, baseline IGA mod 2011, PASI and PROs will be presented as described in [Section 2.3](#).

Other medical history and prior medications and non-drug therapies will not be part of the interim analysis.

3 Sample size calculation

The study aims to estimate primarily the effect of 16 weeks treatment with secukinumab 300 mg on the QoL of the overall study population as well as within the 3 pre-defined subpopulations. It is expected that 40% of the overall study population will fulfil the criteria

for the definition of subpopulation A; 40% will fulfil the criteria for subpopulation B; and 20% will fulfil the criteria for subpopulation C.

The DLQI 0/1 response rate in the overall population treated with secukinumab 300 mg s.c. is expected to be around 70% at Week 16; however, it may vary within those pre-defined subpopulations. A total of 323 patients are required to estimate the response rate of DLQI 0/1 with a precision (= 95% CI) of 5% if the true response rate is about 70% in the smallest subpopulation. To ensure that this precision is achieved in the 3 subpopulations (defined in Section 3.1), which consist of 20% to 40% of the overall study population, 1 615 patients in total should be recruited into this trial.

4 Change to protocol specified analyses

According to the protocol all data from physical examinations should be summarized and listed. As these data are only collected in the source data (see Section 6.5.1 of the protocol) this will not be analyzed.

5 Appendix

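### The SAP treats patients pooled from about 250 centres as independent; if the within-centre correlation exceeds about 0.01, the 95% interval for the overall DLQI 0/1 rate is too narrow

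*SAP*

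**What the plan says.** Protocol 3.1 sets the scale: "The study will take place across Europe, in approximately 250 study centers in 30 European countries". SAP 2.1 states: "Data from all study centers will be pooled for the analysis".

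For the primary endpoint, SAP 2.5.2 says: "For the proportions, (descriptive) 95% CIs will additionally be reported". SAP 5.6.1 gives the method: "Confidence intervals will be derived as well based on the score method including continuity correction". The limits there depend on the normal quantile, the number of patients in the denominator and the crude proportion. There is no centre or country term.

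The sample size (Protocol 9.7, SAP section 3) is a single-proportion precision calculation without a design effect. SAP 2.5.4 plans no sensitivity analysis for the primary endpoint. In the text available, centre appears as a classifier only in the patient count of SAP 2.3.1. SAP 2.7.2.1 and 2.7.2.2 also plan 95% intervals for the DLQI 0/1, PASI and IGA responder rates by visit.

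**The concern.** The score interval is valid for independent patients. Patients at one centre share a setting (hospital or office), a local case mix and an investigator who decides on topical corticosteroid use (Protocol 3.1, 5.5.7.2). Their responses may therefore be positively correlated.

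In a randomised trial much of the centre effect would cancel from the contrast between arms. Here the primary result is an absolute rate, so between-centre variation goes fully into its variance. The interval is the trial's whole statement of uncertainty about that rate. If it ignores a real correlation, an interval labelled 95% covers less often than that. The largest effect is on the overall population, where there are most patients per centre.

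**Working it through.** **Inputs from the documents.** N = 1615 overall, 646 in each of A and B, 323 in C (Protocol 5.2). About 250 centres (Protocol 3.1). For the response rate, SAP section 3 says it "is expected to be around 70% at Week 16; however, it may vary within those pre-defined subpopulations", so p = 0.70.

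**Assumed, because not given.** ICC from 0 to 0.10. Coefficient of variation (CV) of centre size 0, 0.7 or 1.0. All 250 centres open to each subpopulation.

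**1. The plan's own figure.** n = 1.96² × 0.70 × 0.30 / 0.05² = 322.7, so 323; and 323 / 0.20 = 1615. Both reproduce. The 5% is a half-width, and independence is built in.

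**2. The SAP interval at 70%.** Half-widths from the 5.6.1 formula are 2.26 points (n = 1615), 3.60 (n = 646) and 5.13 (n = 323). The simple binomial half-widths are 2.23, 3.53 and 5.00.

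**3. Design effect.** DEFF = 1 + [(1 + CV²)m − 1] × ICC, with m = patients per centre. Overall, m = 1615 / 250 = 6.46. At ICC 0.05:
- CV 0: 1 + 5.46 × 0.05 = 1.27
- CV 0.7: 1 + (1.49 × 6.46 − 1) × 0.05 = 1.43
- CV 1.0: 1 + (2 × 6.46 − 1) × 0.05 = 1.60

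Multiplying 2.23 by the square root of DEFF gives half-widths of about 2.5, 2.7 and 2.8 points, against the 2.26 that would be reported.

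**4. Actual non-coverage of the SAP interval.** Simulated with beta-binomial centre rates, and centre sizes either equal or drawn with gamma weights; 8,000 trials per setting, random error about 0.2 to 0.4 points. Cells give non-coverage in % for equal sizes / CV 0.7 / CV 1.0.

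| ICC | Overall (1615) | A or B (646) | C (323) |
|---|---|---|---|
| 0 | 4.7 / 4.3 / 4.4 | 4.2 / 4.5 / 4.3 | 4.4 / 4.5 / 4.7 |
| 0.01 | 5.1 / 5.6 / 6.6 | 4.7 / 4.6 / 4.5 | 4.9 / 4.4 / 4.5 |
| 0.05 | 7.4 / 10.0 / 11.9 | 5.2 / 6.5 / 7.0 | 5.1 / 5.3 / 6.1 |
| 0.10 | 11.6 / 15.0 / 18.2 | 6.5 / 8.9 / 9.9 | 4.7 / 6.6 / 6.9 |

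A separate simulation of the overall population (40,000 trials per setting) gave 7.5% with equal sizes and 10.6% with CV about 1 at ICC 0.05, and 10.6% and 16.3% at ICC 0.10.

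**5. Where under-coverage starts.** The continuity correction leaves a small reserve. In the 40,000-trial runs, overall coverage was 95.5% at ICC 0 and 95.0% at ICC 0.01 with equal sizes; with CV about 1 it was 95.1% at ICC 0.005. The threshold is therefore an ICC of about 0.01, or somewhat lower if centre sizes are very unequal.

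**6. Planned precision.** The overall half-width would reach 5 points only at DEFF = (5 / 2.235)² = 5.0. In C, m = 323 / 250 = 1.29. At ICC 0.05 and CV 1, DEFF = 1 + (2 × 1.29 − 1) × 0.05 = 1.08, and 5.00 × √1.08 = 5.2 points.

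**7. The proposed interval.** With n replaced by n / max(1, estimated DEFF), simulated overall non-coverage was 4.0% to 5.4% in every setting above. Mean half-widths at ICC 0.05 were 2.56, 2.75 and 2.89 points. At ICC 0 they were 2.30 to 2.32.

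**The case against.** The strongest reply is that nothing in the documents establishes correlation. They give no ICC and no distribution of centre sizes, and they do not say outright whether inference extends beyond the participating centres. If it does not, the binomial interval is not too narrow. This stands as far as certainty goes: a reader might infer that the planned interval is known to under-cover, and the documents do not support that. Against the narrow reading, Protocol 4 and 4.2 aim for a population representative of eligible patients, which points beyond these sites.

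Two features work the other way. The protocol standardises regimen, assessment rules, concomitant psoriasis medication and washout (Protocol 3.2), which should lower the ICC. The fixed 40/40/20 quotas reduce the variance slightly if subpopulation rates differ: rates of 80/70/50% give a variance ratio of 0.94. Neither shows that the ICC is negligible.

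A reader might also infer a rater effect from Protocol 6.4.1: "It is recommended that the same evaluator conducts the assessment throughout the study wherever possible". That does not reach the primary endpoint, because patients complete the DLQI before any investigator assessment (Protocol 6.6.1). Nor does the sentence say that a centre has a single rater. It is at most a possible source of correlation for PASI and IGA.

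Clustering by country is another tempting extension. The documents give no country-level correlation and do not present the countries as a sample, so no figure is claimed here.

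Finally, SAP 5.6.1 says "The primary analysis of this study will be descriptive without any formal group comparisons or hypothesis testing". No decision rests on these intervals and the point estimates do not change. That limits the consequence. It does not remove the expectation that an interval labelled 95% covers about 95%.

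**Conclusion.** The point holds conditionally. The SAP pools about 250 centres and computes its intervals as if patients were independent, and no visible analysis checks this. If the within-centre ICC exceeds about 0.01, the nominal 95% interval for the overall population under-covers: non-coverage is about 7% to 12% at an assumed ICC of 0.05 and 10% to 18% at 0.10. At ICC 0 to 0.01 it is near or below 6%. At ICC 0.05, A and B are at about 5% to 8% and C at about 5% to 6%.

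These figures assume p = 0.70, 250 centres treated as a sample, and the stated spread of centre sizes. It would be wrong to conclude that the sample size is inadequate: C, which determines it, is nearly unaffected, and the overall half-width stays well inside 5 points.

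**What to change.** In SAP 5.6.1, keep the point estimates and the continuity-corrected score formula. Add, at least as a supplementary interval, the same formula with n replaced by n / DEFF, where

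DEFF = max(1, v / (pq/n)) and v = [K/(K − 1)] × Σ(yᵢ − p·mᵢ)² / n².

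Here K is the number of centres contributing patients to the denominator, and yᵢ and mᵢ are the responders and patients at centre i. Set DEFF to 1 when p is 0 or 1.

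Apply it to the DLQI 0/1, PASI and IGA responder rates at Weeks 16 and 52, overall and by subpopulation, and report the estimated DEFF with each. Amend SAP 2.1 to say that centres are pooled for the point estimate and treated as clusters for this interval.

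The cost is SAP wording and a short program. Centre is already held, since SAP 2.3.1 tabulates by it, and no extra patients or data are needed. The overall half-width would be about 2.6 to 2.9 points instead of 2.3 at ICC 0.05, and almost unchanged if there is no clustering.
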